#### **Primary Outcome: Attachment Measure**

The Disturbances of Attachment Interview (DAI; Smyke & Zeanah, 1999) is a semi-structured interview to evaluate the presence of signs of disordered attachment (and is recommended by the NICE Guideline on attachment problems in children in care). For each of 12 sections, the interviewer asks multiple questions and follow-up probes sufficient to yield a rating reflecting degree of evidence of disturbed or disordered attachment: 0 = none/never, 1 = somewhat/sometimes, and 2 = considerable/frequently. The first five sections of the interview address signs of emotionally withdrawn/inhibited attachment disturbance (i.e. RAD), yielding total scores ranging from 0 to 10. The next three items address signs of indiscriminate behaviour, and the last four items address other signs of disturbances in attachment behaviour (known as 'secure base distortions'). There is sound evidence for the validity of this measurement system. First, it distinguishes between institutionalised and non-institutionalised children (Smyke, Dumitrescu, & Zeanah, 2002; Zeanah, Smyke, & Dumitrescu, 2002), reliably identifies signs of attachment disturbance in maltreated children (Zeanah et al., 2004) and validly distinguishes RAD from DSED (e.g., Oosterman & Schuengel, 2007). Second, it has shown very good interrater reliability (Oliveira, Fearon, Belsky, Fachada, & Soares, 2015) and high levels of internal consistency (Smyke et al., 2002; Zeanah et al., 2002). Third, criterion validity has been demonstrated through the convergence of attachment disorder diagnosis by different measurements. Construct validity has also been demonstrated by the association of DAI ratings with quality of care (e.g., Oliveira et al., 2005).

#### **Secondary Outcome Measures**

Attachment insecurity and disorganization

Strange Situation Procedure: Participants will be observed with their foster parent in a laboratory room for the Strange Situation Procedure. The SSP is a standardised procedure, lasting a maximum of 21-minutes. It is divided into a series of episodes involving brief separations and reunions with the parent/caregiver, exposure to an unfamiliar but friendly adult female, and a period of time alone. These episodes are videotaped for subsequent rating by trained coders, resulting in a classification of the infant-parent dyad into one of the four attachment categories: secure, insecure-avoidant, or insecure-resistant and insecure disorganized. For children older than 24 months, an adaptation of the administration of the SSP (mainly concerning timing of each episode) and the respective coding system for the pre-school years will be implemented (Cassidy & Marvin, 1992). Even though the pre-school rating system was originally created for children up to the age of 54 months, we do not anticipate problems in extending it to the 6 year-old participants. Indeed, the pre-school system was created based on the assumption that the "strategies" associated with each one of the three major attachment categories remain the same throughout development. Beyond the classification of attachment categories or patterns, there are additional aspects of behaviour captured by the SSP that can be very informative for understanding the child's socioemotional functioning. Namely, an observation of the child's behaviour toward the stranger and the parent, during the episodes of the SSP, has been used to objectively rate their levels of indiscriminate attachment/social behaviour. The Rating of Infant and Stranger Engagement has been used from 12 months to the pre-school years (Lyons-Ruth, Bureau, Riley, & Atlas-Corbett, 2009). Regarding behaviours indicative of RAD, an observational system based on the SSP episodes is being developed by our collaborators, and will be available for use in this study (known as the Rating of Inhibited Attachment Behaviour (RInAB; Corval, Fachada, & Soares, unpublished manual). This coding system rates the child's attachment, exploratory, and socio-emotional behaviour that is relevant for the conceptualisation of RAD. A continuous score as well as a classification of whether or not the child is considered to present RAD are obtained.

#### **Co-occurring disorder/difficulties**

• *The Development and Well-Being Assessment (DAWBA)* will be used to assess the presence of psychiatric diagnoses co-occurring with RAD, via foster carer interview. The DAWBA is a well-validated diagnostic interview schedule that has been recently extended to children as young as 2 years of age, and has been updated for DSM-5. The DAWBA has been used extensively in clinical trials and epidemiological studies. The system has high-levels of inter-rater reliability and provides automated algorithms for scoring and assigning diagnoses. Note: due to some limitations in its validity for assessing RAD, we rely on the DAI for this diagnosis.

• *Child Behaviour Checklist* (foster carer report): This a very widely used carer-reported questionnaire for assessing children's emotional and behavioural problems and yields well-validated continuous measures of

internalizing problems, externalizing problems, total problems and specific 'syndrome' scales for narrow band symptom areas (such as attention problems, aggression, social problems). It is valid for children from the age of 1.5 years and has age appropriate forms for children aged 1.5-5 years, and 5 years and above.

#### **Broader impact measures**

• *Observed carer sensitivity*: We will use standardized observational procedures for assessing carer sensitivity during free play, and routine caregiving interactions (e.g., a snack, completing a challenging task). The interactions will be video-recorded, and scored blind to treatment condition and status (pre- versus post) by trained researchers. The scoring system used will be the Emotional Availability Scales, which have been extensively validated as indicators of interactions relating to attachment (Biringen, 2000). The interactions will be scored by a reliable coder (certified by the coding system developers). As in all our studies, interrater reliability will be tested on a proportion of cases (minimum 25%).

• *The Parent Stress Index* – Short Form (Abidin, 1990) will be used to assess carer wellbeing, strain and the carer-child relationship.

• *The Parenting Efficacy Scale* ([name] et al., 2012), a measure of beliefs and confidence about parenting skills.

• *Child and Adolescent Service Use Schedule* (CA-SUS; Barrett, Byford, Chitsabesan, & Kenning, 2006); assessing resource use for health economic evaluation.

• Practitioner feedback forms, to provide qualitative feedback about the experience of using VIPP in practice.

This battery of outcome assessments is similar to those we have used in other trials and cohort studies, and our previous experience is that it is not excessively burdensome. However, we will engage in extensive consultation with foster carers (through the carer advisory group) regarding acceptability and burden, and any changes recommend by that group will be implemented. Establishing the optimal balance between participant time /burden and the robustness of the outcome assessments is an important aim of this project as preparation for a full-scale trial.

#### **Time Point**

Measures	Screening	Post-Screening	Post-Screening Baseline			
		interview				
DAWBA	Х		Х	Х		
	(attachment		(excluding SDQ)			
	related items only)					
ASA	Х			Х		
DAI		Х		Х		
		(plus SDQ)				
SSP			Х	Х		
CBCL			Х	Х		
EAS			Х	Х		
PSES			Х	Х		
PSI			Х	Х		
CA-SUS			Х	Х		

Acronyms: DAWBA - The Development and Well-Being Assessment; ASA - Attachment Screening Assessment; DAI - The Disturbances of Attachment Interview; SSP - Strange Situation Procedure; CBCL - Child Behaviour Checklist; EAS - Emotional Availability Scales; PSES - Parenting Self-Efficacy Scale; PSI - Parenting Stress Index; CA-SUS - Child and Adolescent Service Use Schedule; SDQ – Strengths and Difficulties Questionnaire

The research team will attempt to follow-up all families involved in the study, this includes children who have moved to a different placement or who have been given a different care order during the time of the research. Any additional relevant consent that may be required due to placement changes will be obtained (e.g., from the new carer).

# **Process Data and Qualitative Outcomes**

Process data will collected during the pilot RCT to document the uptake, numbers completing treatment, rate and stage of dropout, and acceptability of the treatment to participating families. Records will be kept of the number of families approached and who refuse to take part in the study; data will also be obtained on the range of care pathways observed (e.g., distribution of care orders and placement types, e.g., family and friends care, long-term foster care), numbers moving placements before or after treatment has commenced, and destinations and timing of any movements out of placement). Records will also be kept

of essential information on the child's previous history, such as alleged existence of neglect or abuse and reasons for being taken into care. This data will be obtained from the child's social worker, supplemented with foster carer input and routine social work records. Reasons for refusing to take part in the study, and for dropping out of the intervention will also be examined (see below).

The acceptability data will involve the conduct of qualitative in-depth interviews with all families who received the intervention as part of the pilot RCT (N=20); and brief telephone interviews will be conducted with as many families as possible who refused to take part or who dropped out. The interviews will be conducted at a time of convenience to the participant either in their own home or a setting of their choosing, following the conclusion of the intervention and collection/analysis of post-intervention data. The interviews will be used to examine the factors that facilitated change in those families for whom the quantitative symptom and diagnostic assessments show an improvement in outcome, and the factors that hindered change in those families for whom the quantitative data shows no or some change. Brief telephone interviews will also be conducted with families who did not wish to take part and those families who dropped out, but who are willing to provide consent to take part in these brief telephone interviews. These interviews aim to examine the factors that contributed to their discontinuation with the intervention. The interviews will also be used to explore with families the acceptability of the outcome measures that were utilised.

# 7.3 DATA MANAGEMENT

The data in this study will be collected and processed in accordance with the Data Protection Act (1998). Management of the data will be overseen by the Chief Investigator [name] with support from the Trial Coordinating Team. The case-series and pilot data will be collected by an experienced research assistant who has been trained to work with high-risk populations. The RA will be blind to treatment allocation, with all data issues related to unblinding being handled by the Trial Coordinating Team. Regular supervision with the Chief Investigator, Trial Coordinating Team and core study team (RAs) will ensure the reliability of data collection. Where necessary the RAs will be fully trained and certified in administering all research measures. For data that requires coding using standardized measures we will employ trained reliable coders, ensuring sufficient Inter-Rater Reliability (IRR) amongst coders.

# 7.4 DATA STORAGE

Although a number of NHS Trusts and higher education institutions are involved in this study, all data will be collected, collated and stored at UCL. Information that the family will be taking part in the trial and the

treatment arm to which they are allocated (either CAU and VIPP-FC or CAU only) in the pilot trial (phase 3) will be communicated to the local authority and intervention provider. Any other data shared will be in an anonymised format (e.g. for analysis at Imperial College).

#### Paper documents

Data collected at all stages will be recorded as a hard copy on paper. The paper forms, along with other paper documents such as consent forms and letters, will be stored in a locked cabinet at UCL, accessible only to members of the research team. These will contain identifiable data as carers will need to provide contact details when returning the screening forms. In the event of participant withdrawal we will seek approval to retain the data previously collected on the participant. If the participant would like to withdraw and to have all data collected removed from the study then we will respect their decision. However, in the event where participants are lost to follow-up and we are unable to contact them, we would proceed to use their collected data consistent with their most recently signed consent.

#### Database

Data for phase 3 (pilot trial) will then be transcribed onto the trial specific database by the RA. The database will be built using REDCap, a secure web application for building and managing online surveys and databases. Data entered onto the database will be anonymised, with participants identified by a randomisation code and no information that could be used for identification included (e.g. date of birth). A master log of participants that are randomised will be kept as a paper document in the Trial Master File, detailing names and randomisation code. The Trial Master File will also be stored in a locked cabinet at UCL, separate from the participant files and accessible only to members of the trial coordination team and Chief Investigator.

## Identifiable data (video and audio recordings)

As part of the study procedures, audio recordings will be made of participants during VIPP-FC session and as part of phase 2b. Video recordings are also made during the VIPP-FC sessions and research assessments. These recordings will be stored within the UCL data safe haven or Citrix, two secure and accredited technical solutions for storing, handling and analysing identifiable data that conform to the NHS Information Governance Toolkit. A standard operating procedure will describe the process of transferring the file from the recording device, ensuring that it is stored correctly and then deleted from the recording device.

# 8 END OF TRIAL

The study is planned to run for 30 months. Overall, participant involvement will be no longer than 6 months. The end of trial will be the last patient, last visit of phase 3 (pilot trial).

# 9 ARCHIVING

Good clinical practice compliant archiving will be completed for the trial master file and all other essential documents, including all those relating to the participants. This will be done following submission of the end of trial report to the REC, and according to UCL archiving procedures. The files will be archived for 10 years.

# **10** ANALYSIS

Feasibility parameters based on proportions (proportions of cases identified, consented, randomised, completing treatment and outcome measures). Approximate variance estimates will be obtained for the main outcome measures using the upper 80th percentile of the relevant confidence interval (see Brown, 1995). Specifically, we will test the following feasibility parameters:

A. Test the feasibility of identifying sufficient numbers of appropriate cases using screening instruments.

1. Target N for screening tests returned N = 500. Test a.1 = proportion and 95% CI of those returning screening instruments from total sent out.

2. Target N of diagnostic assessments N = 100. Test a.2 = proportion and 95% CI of positively screened cases (above upper 66th percentile) agreeing to full assessment.

3. Target N for positive diagnosis from upper 66th percentile of screened cases N = 50. Test a.3 = proportion and 95% CI of cases where diagnosis is confirmed.

4. Test a.4: initial test of false negative rate = proportion (of 25 cases) and 95% CI of detected diagnoses in random sample of cases not meeting screening threshold.

5. Initial non-parametric ROC curve analysis (total N = 125), based on assumption that DAI diagnosis is gold standard.

B. Test the feasibility of recruiting/consenting foster families with children with RAD to an RCT.

1. Target N of consented cases N = 40. Test b.1 = proportion and 95% CI of cases consenting to enter pilot trial from those meeting entry criteria.

C. Investigate feasibility of randomising to VIPP-FC or CAU.

1. Test c.1: proportion and 95% CI of cases accepting randomisation.

D. Document study throughput.

1. Test d.1: proportion and 95% CI of cases randomised completing treatment (definition of completing= 80% of offered sessions).

2. Test d.2: proportion of cases attending each session (6 proportions and 95% CIs).

4. Acceptability of treatment: means and ranges of client satisfaction survey. See also qualitative methods for client experience of treatment interviews.

E. Establish the feasibility and acceptability of baseline and outcome assessments.

1. Test e.1: proportion and 95% CI of cases with complete data. See also qualitative methods for client feedback regarding measures.

F. Identify the most appropriate primary outcome. Key assessment is participant feedback from qualitative interviews. However preliminary tests from H.2 below may also be informative.

G. Obtain initial estimates of variance of key outcome measures and constrain effect size estimates for future power analyses.

- 1. Test h.1: S.D. of RAD symptom counts and 95% CI.
- 2. Test h.2: Mean post-treatment group difference and 95% CI (though please see point 8 above).

H. Establish the optimal and most acceptable screening tools for RAD as recently redefined in DSM-5. Tested with qualitative interviews and tests a.4 and a.5 above.

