#### Pilot RCT

For Phase 3 (the pilot RCT) we will again undertake a screening process to identify children in foster care with RAD. We will then randomise 40 children (and their carers) to receive either VIPP (plus care as usual) or care as usual only. Based on data obtained from the Department of Education from 2014 (which we have corroborated against a selection of figures obtained in 2016 from our participating local authorities) we expect the full population of children in foster care in our target age groups across sites to be in the region of 700. Previous research experience with this population and on the basis of our small pilot screening, we would expect more than 80% of foster carers to take part in the initial screening and return the questionnaires. This estimate seems reasonable, since in the study of Green et al. (2014) of 523 foster families who were approached, only 56 refused (a further 57 were ineligible). Conservatively therefore we will aim for a sample size for the screening stage of 500. In order to identify cases likely to be diagnosed as RAD we will choose cases above the highest 66th percentile for symptoms of RAD (initially based on normative data), leading to a sample size of 150 who would be invited to take part in a more in-depth assessment. We expect a minimum of two thirds of those to agree to take part and complete the assessment. In the randomised controlled trial of the Fostering Changes programme, (Briskman et al., 2012) 77/125 took part in the intervention (following a higher rate of initial interest and questionnaire return), so two-thirds agreeing to an initial assessment is a conservative estimate. From this pool of 100 children we would therefore have scope to identify at least 40 cases that would be eligible for treatment as long as the prevalence of RAD in the high-scoring screened group was 50% (allowing for a further 10% dropout at this stage). Note that we would seek to obtain consent to treatment at the in-depth intake assessment stage, which is why we estimate the throughput of cases to be lowest at this point. As noted already, we lack reliable information concerning the prevalence of RAD in UK foster care and so the 50% prevalence within the population of children exceeding the symptom threshold is subject to uncertainty. Consequently, we propose an interim analysis after 15 cases have been assessed to establish whether the proportion of RAD cases is below this expected proportion. The lower bound of the 95% confidence interval around a proportion of .50 is .22 with a sample size of 15. Thus, identification of fewer than 3 cases out of 15 would suggest that the prevalence is lower than .50. In this event, we propose to widen the eligibility criteria to include children scoring over the screening threshold, but not meeting full RAD diagnostic criteria.

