As the screening/identification stage (which consists of a postal and/or an online survey and carer interview) involves no direct contact with the child and involves minimal burden or risk, we will only obtain active consent from the foster carer. However, a letter will be sent to all parents with an explanation of the study and the process of opting-out (except in circumstances where the local authority deems this inappropriate). If after the two-week period for opting-out the Local Authority or the research team has not been contacted by the parent to opt-out, the screening process will be initiated. Foster carers will receive an information sheet explaining the study fully, and a contact telephone number of a member of the research team if they have any questions. The information sheet will explain that completing the screening measures does not entail any obligation to participate in the other stages of the study (the pilot intervention). Written consent will be provided on the consent form (completed by the carer but not a member of the research team at this stage) and posted to the research team along with the screening questionnaires. The study team will receive email notifications from the study database when a participant

gives consent and completes the questionnaires online. Both paper and online consent forms will require the carer to provide their contact details (including the child's initials) in order for the research team to contact them if they meet the screening cut-off. Carers will be given a £10 voucher to thank them for completing the screening questionnaires.

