# 7.2 MEASURES FOR TEST CASE SERIES (PHASE 2A) AND PILOT RCT (PHASE 3)

#### **Screening Measures**

The process of screening of symptoms of RAD is not straightforward, and no fully validated instruments for this purpose exist. This in itself is a significant gap in health technology in this field, as early detection may be critical for improving outcomes for children in care. We propose to use two different instruments that each have their individual limitations, but should make it possible to robustly screen for symptoms of RAD when used together. *The Attachment Screening Assessment* is a new instrument designed specifically to
capture behaviours reflective of the DSM-5 symptoms of RAD and DSED, as well as attachment classifications. The RAD items in particular therefore have greater face validity than the other widely used instrument, the Relationship Problems Questionnaire (RPQ), and have also been found to discriminate well between children in care and those from the community, as well as children with greater overall psychopathology on the SDQ. However, the ASA has thus far not been validated against formal diagnostic assessments, which limits the extent to which it could be used alone as a screening measure. *The Development and Well-Being Assessment (DAWBA)* includes a recently revised set of diagnostic items for DSM-5 RAD. We propose to use these two instruments so that we can test the optimal configuration of items for case identification. This will be achieved through expert consensus and will be combined with adaptive prediction methods as data comes in (specifically, adjusting item weights based on accumulating data from full diagnostic assessments). Since this is a feasibility trial we believe this to be the best way of approaching the uncertainty about the optimal screening tools in this area.

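### Test a.4 labels the false omission rate (1 − NPV) as a false negative rate, and test a.5 combines two groups verified at very different rates without saying how this is handled

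*Protocol*

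**What the plan says.** Section 10 (Analysis), part A, sets out how the screen will be judged.

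- Screening volume: "Target N for screening tests returned N = 500".
- Screen-positives: section 6.1 (Pilot RCT) takes children above a high percentile, "leading to a sample size of 150 who would be invited to take part in a more in-depth assessment". It adds: "We expect a minimum of two thirds of those to agree to take part and complete the assessment". Section 10 carries this forward as "Target N of diagnostic assessments N = 100", with 50 confirmed diagnoses as the target in a.3.
- Test a.4: "false negative rate = proportion (of 25 cases) and 95% CI of detected diagnoses in random sample of cases not meeting screening threshold".
- Test a.5: "Initial non-parametric ROC curve analysis (total N = 125), based on assumption that DAI diagnosis is gold standard".

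Part H of section 10 then answers the screening-tool objective (objective J in section 4.2) from qualitative interviews together with a.4 and a.5. Section 7.2 (Screening Measures) also foresees "adjusting item weights based on accumulating data from full diagnostic assessments".

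**The concern.** The two tests have different faults.

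In a.4 the label and the definition do not match. The definition conditions on the screening result: among children the screen let through, how many have RAD? A false negative rate conditions on disease: among children with RAD, how many did the screen let through? When screen-negatives greatly outnumber cases, the first figure is much smaller than the second.

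In a.5 the stated total of 125 brings together two groups that reach the diagnostic interview (the Disturbances of Attachment Interview, DAI) at very different rates, and the rate depends on the screening result itself. A ROC curve computed on the pooled 125 as if they were one random sample has verification bias.

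At stake is the choice of screen for the future trial. A reported 4% or 8% for missed cases could support a tool that misses several times that share.

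**Working it through.** **Inputs from the protocol.** 500 screened; 150 screen-positive; 100 of these assessed; 50% RAD among positives (section 6.1, and 50 of 100 in section 10); 25 screen-negatives assessed.

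**Derived.** Screen-negatives: 500 − 150 = 350. Expected RAD cases among all positives: 150 × 0.5 = 75.

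**Assumed.** The number of diagnoses among the 25 is not given anywhere, so a range is shown.

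**The plan's own figures.** The ROC total reproduces as 100 + 25 = 125. The section 6.1 intervals reproduce with the exact Clopper-Pearson method (30/40 gives 58.8% to 87.3%, stated as 59% to 87%), so the same method is used for a.4.

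**Test a.4.** With q the proportion found in the 25:

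false negative rate = 350q / (350q + 75)

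| Diagnoses in 25 | a.4 as defined (q) | Missed cases, 350q | False negative rate |
|---|---|---|---|
| 1 | 4% | 14 | 14/89 = 15.7% |
| 2 | 8% | 28 | 28/103 = 27.2% |
| 3 | 12% | 42 | 42/117 = 35.9% |
| 5 | 20% | 70 | 70/145 = 48.3% |

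The label understates the miss rate by a factor of 3.9 (15.7/4) at 1/25, falling to 2.4 (48.3/20) at 5/25. With 0/25 the upper 95% limit for q is 13.7%. Then 350 × 0.137 = 48, and 48/(48 + 75) = 39%.

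Two inputs were varied:
- If the percentile rule is read literally as the top 34%, the split is 170/330 and cases among positives are 85. The rates for 1, 2 and 3 in 25 become 13.4%, 23.7% and 31.8%.
- If RAD among positives is 20% rather than 50%, cases among positives are 30. The rates become 14/44 = 31.8%, 28/58 = 48.3% and 42/72 = 58.3%.

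**Test a.5.** Verification fractions are 100/150 = 67% and 25/350 = 7.1%, so the inverse weights are 1.5 and 14. At the screening cut-off:

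| Diagnoses in 25 | Sensitivity, unweighted | Sensitivity, weighted | Specificity, unweighted | Specificity, weighted |
|---|---|---|---|---|
| 1 | 50/51 = 98.0% | 75/89 = 84.3% | 24/74 = 32.4% | 336/411 = 81.8% |
| 2 | 50/52 = 96.2% | 75/103 = 72.8% | 23/73 = 31.5% | 322/397 = 81.1% |
| 3 | 50/53 = 94.3% | 75/117 = 64.1% | 22/72 = 30.6% | 308/383 = 80.4% |

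**AUC.** This needs a model for the score. Under an equal-variance binormal score with 30% screen-positive and 50% RAD among positives, the population AUC for q = 4%, 8% and 12% is 0.912, 0.854 and 0.805. The unweighted pooled analysis tends to 0.848, 0.789 and 0.745. The weighted estimate averages 0.917, 0.859 and 0.813 over 3,000 simulated samples, with standard deviations of 0.050, 0.064 and 0.069.

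**The case against.** The strongest reply is that a.4 states its numerator and denominator beside the label, so no data are lost and a careful reader could derive the true false negative rate from a.1 to a.4. That is correct, and it makes this an error of definition rather than of design. It does not rescue the label: the figure reported under that name would be the wrong quantity.

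Several stronger readings are tempting, and the protocol does not support them.

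- *That a.4 also pools the two groups.* It uses only the 25 screen-negatives. Its fault is the denominator; only a.5 combines groups.
- *That the protocol commits to an unweighted ROC.* It is silent on weighting, and an analysis plan could specify it. The a.5 part is therefore conditional; the a.4 part is not.
- *That a re-tuned score will be judged on the data that tuned it.* Section 7.2 describes adaptive item weights alongside expert consensus, but no text says a.5 evaluates the re-tuned score on the same interviews. This is a risk to guard against, not a stated error.
- *That the 25 have no route to the interview.* Section 6.2 asks for contact details "in order for the research team to contact them if they meet the screening cut-off", but does not say that others will not be contacted. It also has the team contact respondents once forms are returned, and requires only the foster carer's active consent for the DAI. The recruitment figure is not shown. At most, the approach to these 25 is not described in the visible text.
- *That this endangers the trial.* Both tests are called initial, and interviews contribute to the same objective. None of the numerical progression thresholds in section 13.1 (treatment retention, outcome completion, RAD identification rate) uses a.4 or a.5.

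It is also fair to say that weighting buys less bias at the price of variance. In the simulation the standard deviation of the weighted AUC (0.050 to 0.069) is about as large as the bias removed.

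**Conclusion.** Test a.4 is wrong as written: it names one quantity and defines another. In every non-zero scenario examined, the defined quantity is the smaller, about a quarter to two fifths of the false negative rate at 50% RAD among positives. The size rests on the derived 350 negatives, on the 50% figure (which section 6.1 itself calls uncertain) and on assumed counts in the 25. A lower RAD rate among positives widens the gap.

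For a.5 the conclusion is conditional. If the 125 are analysed without weights, sensitivity at the cut-off is overstated and specificity severely understated. The AUC is also likely to be biased. It was lower by roughly 0.06 in the three scenarios above, but that amount belongs to the assumed model.

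Severity is moderate. The choice of screening tool is affected; progression thresholds and the randomised comparison are not.

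**What to change.** 1. Rename a.4 as the proportion of screen-negatives with RAD, 1 − NPV (false omission rate), keeping its definition and interval.
2. State that the false negative rate, sensitivity, specificity and ROC/AUC are estimated by weighting both groups back to all screened children with the observed verification fractions (Begg-Greenes). Confidence intervals should reflect sampling in both groups, for example a bootstrap within each group. Note the assumption that, within each group, children assessed represent those not assessed; this matters for the third of screen-positives expected not to complete the assessment.
3. If a.5 is applied to a score whose item weights were tuned on the same DAI data, report an optimism-corrected AUC (bootstrap or cross-validation).

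The cost is a few sentences in section 10 and no new assessments. The real downside is imprecision, because each of the 25 negatives carries a weight of about 14. At 1/25, carrying only the interval for q through the formula with RAD among positives fixed at 50%, the false negative rate runs from about 0.5% to 49%. That width is what 25 children can support, and it should be shown.
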